15 QUALITY CONTROL AND ASSURANCE

Quality review activities will be undertaken to ensure accurate, complete, and reliable data. The sponsor and/or its representatives will do the following:

- Provide instructional material to the study sites, as appropriate.
- Conduct a start-up training session (investigator meeting or study initiation visit) to instruct the investigators and study coordinators. This session will give instruction on the protocol, the completion of the eCRFs, and study procedures.
- Make periodic visits to the study site to monitor protocol compliance and general GCP compliance.
- Be available for consultation and stay in contact with the study site personnel by mail, e-mail, telephone, and/or fax.
- Review and evaluate eCRF data and use standard computer checks to detect and query errors in data collection.
- Conduct a quality review of the database.

15.1 Monitoring, Auditing, and Inspections

To ensure participant safety in the study, compliance with applicable regulations, and ensure accurate, complete, and reliable data, the investigator will keep records of laboratory tests, clinical notes, and medical records in participant files as source documents for the study.

The sponsor or its designee will monitor the study on a regular basis throughout the study period. The investigator will allocate adequate time for such monitoring activities. The study monitor periodically will conduct a cross-check of participant data recorded on eCRFs against source documents at the study site. The sponsor or designated monitor will review study pharmacy and medical records according to the clinical monitoring plan. The investigator will also ensure that the designated study monitor is given access to all the above noted study-related documents, source documents (regardless of media) and study-related facilities (e.g., investigational pharmacy, etc.), and has adequate space to conduct the monitoring visit. Queries may be raised if any data are unclear or contradictory. The investigator and study site personnel must address all queries.

Participation as an investigator in this study implies acceptance of the potential for inspection by the study sponsor or representatives, US or non-US government regulatory authorities, IRB of record, and applicable compliance and quality assurance offices. The investigator will permit study-related audits and inspections and will provide access to all study-related documents (e.g., source documents, regulatory documents, data collection instruments, study data, etc.). The investigator will ensure the capability for inspections of applicable study-related facilities (e.g., pharmacy, diagnostic laboratory, etc.).

15.2 Data Collection and Management

Site personnel will record all data through eCRFs using an electronic data capture (EDC) system provided and approved by the sponsor. Additional information, if any, regarding eCRFs used as source documentation will be provided by the sponsor. Study sites must complete eCRFs after each participant visit per the eCRF completion guidelines. The investigator must sign the investigator statement in each eCRF.

The EDC system automatically generates queries resulting from the computer edit checks embedded into the system to ensure data accuracy, quality, consistency, and completeness. Manual queries resulting from review by study and medical monitors, medical coders, and data management staff are also generated from within the EDC system. Study sites are expected to resolve the queries and correct the entered data accordingly. Every change to data is captured in the EDC system audit trail. Upon completion of the study, or after reaching a pre-specified point in the study, data management will lock the database and generate the SAS datasets necessary for analysis and reporting. Each study site will receive the eCRFs for each of their participants.

16 ADMINISTRATIVE CONSIDERATIONS

16.1 Institutional Review Board

The study protocol, any related documents, and participant-facing materials will be submitted to the IRB of record for review and approval. Written approval of the study protocol and the informed consent forms (ICFs) will be in the possession of the investigator and the sponsor before the study drug is shipped to the investigator's site. This approval must include the date of review, the protocol title and/or study number and version number, and ICF version number or date. A stamped version of the IRB of record-approved consent is acceptable. If the IRB of record or institution uses its own unique number for the protocol instead of the sponsor's number, that unique number should be noted on the approval statement. The investigator should provide the sponsor with a statement of compliance from the IRB of record indicating compliance with the applicable regulations in the region and ICH.

Protocol modifications or changes may not be initiated without approval from the sponsor and prior written IRB of record approval (when required), except when necessary to eliminate immediate hazards to participants. Such modifications will be submitted to the IRB of record; and written verification that the modification was submitted should be obtained. The investigator must submit all changes and updates to required documents to the IRB of record.

16.2 Ethical Conduct of the Study

The investigational study will be conducted according to the Protection of Human Subjects (21 CFR [Code of Federal Regulations] 50), Institutional Review Boards (21 CFR 56), Obligations of Clinical Investigators (21 CFR 312.60 – 312.69), the current ICH Guideline for Good Clinical Practice (ICH E6), Office for Human Research Protections (45 CFR 46), and all other applicable regulations.

16.3 Participant Information and Consent

The investigator will obtain, document, and retain IRB or record-approved written informed consent from the participant, as specified in [Section 9.2](#). Where required, the investigator will use an appropriately translated and IRB of record-approved version. The sponsor reserves the right to delay initiation of the study at a site where ICFs do not meet the standards of applicable local regulations or ICH E6.

Information should be given to the participant in both oral and written form, and participants must be given ample opportunity to inquire about details of the study. The ICF must be signed and dated by the participant, and by the person who conducted the discussion of the informed consent.

All versions of each participant's signed ICF must be kept on file by the investigator for possible inspection by regulatory authorities and/or authorized sponsor personnel.

16.4 Participant Confidentiality

To maintain participant confidentiality, all laboratory specimens, evaluation forms, reports, and other records will be identified by a coded number. Clinical information will not be released without written permission of the participant, or the participant's legally authorized representation, except as necessary for monitoring by the relevant regulatory authorities, the sponsor, or the sponsor's representative. The investigator must comply with all local applicable privacy regulations regarding the protection of participant data.

16.5 Source Documents

Source data in a clinical study are the original records or certified copies where clinical observations are first recorded, which may include, but are not limited to, the participant's medical file, original laboratory reports, histology, and pathology reports (as applicable). The investigator is responsible for maintaining adequate and accurate medical records from which accurate information will be entered into the eCRFs.

16.6 Retention of Data

All essential documents, including eCRFs, source documents (regardless of media), and signed ICFs, should be retained by the investigator, per the guidance in ICH E6 or other regulatory retention requirements. There may be other circumstances for which the sponsor is required to maintain study records for longer periods; therefore, the sponsor should be contacted before study records are removed from the control of the study site for any reason. The investigator must obtain written permission from the sponsor prior to destruction of study documents.

16.7 Sample Retention and Secondary Research

Samples acquired for protocol-specified assays are retained according to local and regional regulatory requirements. If the participant consents, or the participant's legal representative consents, to the use of their study samples for secondary research purposes, samples may be used for exploratory testing and retained up to 15 years from the end of study.

16.8 Financial Disclosure

The investigator and sub-investigators are required to disclose in writing any applicable financial arrangement as defined in US regulation. The investigator's disclosure will be signed and dated prior to participating in the study.

The information, as defined in 21 CFR 54, will be collected about the investigators, their spouses and each dependent child. Investigators must update the sponsor with any changes in reported information up to 1 year following the end of the study.

In accordance with US Securities and Exchange Commission regulation (17 CFR 229.404), investigators and sub-investigators must disclose if they are employees of the sponsor, or if an immediate family member of a sponsor employee, officer, or board director.

16.9 Publication and Disclosure Policy

Data collected in this clinical study belong to the study sponsor. The publication terms regarding use of study data are noted in the clinical trial agreement. This includes authorship; scheduling and prioritizing analyses for reports, publications, and presentations; and developing a review and approval process.

16.10 Discontinuation of the Study or Study Sites

Site participation may be discontinued by the sponsor, the investigator, a regulatory authority, or the IRB of record. The study may be discontinued by a regulatory authority or at the discretion of the sponsor.

16.11 Identification of the Coordinating Principal Investigator

is the coordinating principal investigator for this study.

The coordinating investigator's responsibilities include review of the final CSR. Agreement with the final CSR is documented by the dated signature of the coordinating principal investigator.

Appendix 1 Time and Events Schedules

Table 7 Time and Events Schedule (Part 1A and Part 1B)

Procedure	Screening ^a	Dosing	Follow-up Period							End of Study ^b
			1	2	3	4	5	6	7	
Visit	Screen	1								8
Study Day	Day -56 to -1	Day 1	Day 2	Day 3	Day 8 (± 2 days)	Day 15 (± 2 days)	Day 22 (± 2 days)	Day 29 (± 2 days)	Day 43 (± 3 days)	
Study Drug Administration										
MGD020 infusion (Part 1A and Part 1B) ^c		X								
MGD014 infusion (Part 1B only)		X								
Clinical Procedures										
Informed consent	X									
Inclusion/exclusion criteria	X									
Enrollment	X									
Medical history	X									
Demographics	X									
Physical examination ^d	X	X	X	X	X	X	X	X	X	
Vital signs ^e	X	X	X	X	X	X	X	X	X	
Weight	X	X								
Height	X									
ART adherence	X	X	X	X	X	X	X	X	X	
Concomitant medications	X	X	X	X	X	X	X	X	X	
ECG ^f	X	X								X
Adverse events ^g	X	X	X	X	X	X	X	X	X	
Clinical Laboratory Collection ^h										
Hematology	X	X ⁱ	X		X		X		X	
Chemistry	X	X ⁱ	X		X		X		X	
Coagulation	X									X
Urinalysis	X									X
Pregnancy test ^j	X	X ^j							X	X
Optional FSH	X									
CD4/CD8	X									X
HIV-1 PCR viral load	X									X

Table 7 Time and Events Schedule (Part 1A and Part 1B)

Procedure	Screening ^a	Dosing	Follow-up Period							End of Study ^b
			1	2	3	4	5	6	7	
Visit	Screen	Day 1	Day 2	Day 3	Day 8 (± 2 days)	Day 15 (± 2 days)	Day 22 (± 2 days)	Day 29 (± 2 days)	Day 43 (± 3 days)	
Study Day	Day -56 to -1									
Rapid plasma reagin	X									
Hepatitis B surface antigen	X									
HCV antibody or RNA ^k	X									
Research Laboratory Sample Collection										
PK/ADA/PD/cytokines/HLA	See Table 9 (Part 1A) or Table 10 (Part 1B) in Appendix 2									

- a Results of standard-of-care tests or examinations performed prior to obtaining informed consent and within the 56 day window may be used for screening.
- b If a participant is unable to complete the study, but has not withdrawn consent, the end of study visit (EOSV) is conducted 30 days (+3 day window) after the last dose of study drug(s).
- c MGD020 is infused first on days when both MGD020 and MGD014 are administered (Part 1B only).
- d Full physical exams are performed at screening and EOSV. All other physical exams are directed physical exams based on signs and symptoms, and as clinically indicated.
- e At the dosing visit, vital signs are measured pre-infusion; at 15 and 30 min after start of infusion (± 5 min); at end of infusion (EOI) of all study drug(s) (± 5 min); at 15, 30, 45, and 60 min post-infusion of last study drug (± 5 min); then every 60 min (± 10 min) until 6 hours after EOI or until the end of the monitoring period (see [Section 6.5.1](#)), whichever comes first. For participants on Parts 1A and 1B, vital signs are also measured at 10 hours (± 10 min) after the EOI. At non-dosing in-person visits, vital signs are assessed once.
- f ECGs are performed in triplicate (approximately 1 min apart). At screening and EOSV, ECGs will be taken at one time point. At the dosing visit (Day 1), ECG is recorded pre-infusion, at EOI of all study drug(s), at 30 and 60 min after EOI of last study drug, and as clinically indicated. ECGs after EOI have a ± 10 min window.
- g Assess participants for adverse events. Participants are also instructed to contact the study coordinator or investigator if any signs or symptoms of an AE occur at any time during the study.
- h Additional and/or more frequent safety laboratory tests may be performed as clinically indicated per the investigator's discretion.
- i Clinical laboratory assessments scheduled for Day 1 can be obtained within 7 days prior to infusion. See [Section 9.11](#) for detailed list of assessments. Indirect bilirubin is required if participant on atazanavir.
- j Participants of childbearing potential only. Serum pregnancy test is required at screening. Subsequent pregnancy tests may use serum or urine. Results must be reviewed before study drug infusion. If screening test is performed within 72 hours of study drug infusion, repeat testing on Day 1 may be deferred.
- k Reflex HCV PCR viral load test is performed only if positive for HCV antibody.

Abbreviations: ADA: anti-drug antibody; ART: antiretroviral therapy; CD: cluster of differentiation; ECG: electrocardiogram; EOI: end of infusion; EOSV: end of study visit; FSH: follicle stimulating hormone; HCV: hepatitis C virus; HIV-1: human immunodeficiency virus-1; HLA: human leukocyte antigen; PCR: polymerase chain reaction; PD: pharmacodynamics; PK: pharmacokinetics.

Table 8 Time and Events Schedule (Part 2)

Procedure	Screening ^a	Dosing Period						Follow-up Period			End of Study ^b
		1	2	3	4	5	6	7	8	9	
Visit	Screen	Day 1	Day 2	Day 4	Day 8 (± 1 day)	Day 15 (± 1 day)	Day 29 (± 1 day)	Day 43 (± 2 days)	Day 50 (± 2 days)	Day 64 (± 3 days)	Day 78 (± 3 days)
Study Day	Day -56 to -1										
Study Drug Administration											
MGD020 infusion ^c		X				X	X				
MGD014 infusion		X				X	X				
Clinical Procedures											
Informed consent	X										
Inclusion/exclusion criteria	X										
Enrollment	X										
Medical history	X										
Demographics	X										
Physical exam ^d	X	X	X	X	X	X	X	X	X	X	
Vital signs ^e	X	X	X	X	X	X	X	X	X	X	
Weight	X	X				X	X				
Height	X										
ART adherence	X	X	X	X	X	X	X	X	X	X	
Concomitant medications	X	X	X	X	X	X	X	X	X	X	
ECG ^f	X	X				X	X				X
Adverse events ^g	X	X	X	X	X	X	X	X	X	X	
Optional leukapheresis ^h	X ^h							X ^h			
Clinical Laboratory Collectionⁱ											
Hematology	X	X ^j				X	X	X ^k			X
Chemistry	X	X ^j				X	X				X
Coagulation	X										X
Urinalysis	X										X
Pregnancy test ^l	X	X ^l				X	X			X	X
Optional FSH	X										
CD4/CD8	X										X
HIV-1 PCR viral load	X										X
Rapid plasma reagin	X										
Hepatitis B surface antigen	X										

Table 8 **Time and Events Schedule (Part 2)**

Procedure	Screening ^a	Dosing Period						Follow-up Period			End of Study ^b
		1	2	3	4	5	6	7	8	9	
Visit	Screen	Day 1	Day 2	Day 4	Day 8 (± 1 day)	Day 15 (± 1 day)	Day 29 (± 1 day)	Day 43 (± 2 days)	Day 50 (± 2 days)	Day 64 (± 3 days)	Day 78 (± 3 days)
HCV antibody or RNA ^m	X										
Research Laboratory Sample Collection											
PK/ADA/PD/cytokines/HLA	See Table 11 in Appendix 2										

- a Results of standard-of-care tests or examinations performed prior to obtaining informed consent and within the 56 day window may be used for screening.
- b If a participant is unable to complete the study, but has not withdrawn consent, the end of study visit (EOSV) is conducted 30 days (+3 day window) after the last dose of study drug(s).
- c MGD020 is infused first on days when both MGD020 and MGD014 are administered.
- d Full physical exams are performed at screening and EOSV. All other physical exams are directed physical exams based on signs and symptoms, and as clinically indicated.
- e On dosing visits (Day 1, 15, and 29), vital signs are measured pre-infusion; at 15 and 30 min after start of infusion (± 5 min); at end of infusion (EOI) of all study drug(s) (± 5 min); at 15, 30, 45, and 60 min post-infusion of last study drug (± 5 min); then every 60 min (± 10 min) until 6 hours after EOI or until the end of the monitoring period (see [Section 6.5.1](#)), whichever comes first (until 2 hours after EOI on Day 15 and 29). During non-dosing in-person visits, vital signs are assessed once.
- f ECGs are performed in triplicate (approximately 1 min apart). At screening and EOSV, ECGs will be taken at one time point. On dosing visits (Day 1, 15, and 29), ECG is recorded pre-infusion, at EOI of all study drug(s), at 30 and 60 min after EOI of last study drug, and as clinically indicated. ECGs after EOI have ± 10 min window.
- g Assess participants for adverse events. Participants are also instructed to contact the study coordinator or investigator if any signs or symptoms of an AE occur at any time during the study.
- h Optional leukapheresis is performed only after the participant is enrolled in the study. If the participant consents to this optional procedure, a baseline leukapheresis is completed. If a baseline leukapheresis was performed, a second leukapheresis procedure is completed 2 weeks (+2 week window) following the final study drug infusion.
- i Additional and/or more frequent safety laboratory tests may be performed as clinically indicated per the investigator's discretion.
- j Clinical laboratory assessments scheduled for Day 1 can be obtained within 7 days prior to infusion. See [Section 9.11](#) for detailed list of assessments. Indirect bilirubin is required if participant on atazanavir.
- k Day 43 hematology is assessed only for participants undergoing leukapheresis. This hematology assessment is performed within the window for the scheduled leukapheresis.

- 1 Participants of childbearing potential only. Serum pregnancy test is required at screening. Subsequent pregnancy tests may use serum or urine. Results must be reviewed before study drug infusion on Day 1, Day 15, and Day 29. If screening test is performed within 72 hours of first infusion, repeat testing on Day 1 may be deferred.
 - m Reflex HCV PCR viral load test is performed only if positive for HCV antibody.

Abbreviations: ADA: anti-drug antibody; ART: antiretroviral therapy; CD: cluster of differentiation; ECG: electrocardiogram; EOI: end of infusion; EOSV: end of study visit; FSH: follicle stimulating hormone; HCV: hepatitis C virus; HIV-1: human immunodeficiency virus-1; HLA: human leukocyte antigen; PCR: polymerase chain reaction; PD: pharmacodynamics; PK: pharmacokinetics.

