4.3 Dose-Limiting Toxicity

DLT is defined based on treatment-related AEs that occur during the DLT period following study drug administration. The DLT period is defined as the period from initial infusion of study drug(s) through 2 weeks following the last study drug infusion.

Severity of AEs is graded according to the National Institute of Allergy and Infectious Diseases (NIAID) Division of Acquired Immunodeficiency Syndrome (DAIDS) Table for Grading the Severity of Adult and Pediatric Adverse Events, corrected version 2.1, July 2017 (see [Section 12.1.6](#)).

A DLT is any \geq Grade 2 treatment-related AE, with the following exceptions, based on the medical judgement of the investigator (or designee) and medical monitor:

- Grade 2 laboratory abnormality that lasts $<$ 72 hours and is not otherwise associated with clinical complications.
- Grade 2 fatigue that lasts $<$ 7 days.

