4.4.1 Dose Delays

Hold study drug administration for toxicity, pending assessment, management, and resolution of the AE. If the AE is assessed as unrelated to study drug(s) or does not meet DLT criteria, study drug(s) may be restarted at the previous dose and schedule, after appropriate recovery.

In Part 2, a dose delay of up to 7 days is allowed for drug-related or non-drug related AEs. Refer to [Section 7.1](#) for specific guidance on restarting study therapy after infusion reactions. A dose delay $>$ 7 days due to drug-related toxicity will prompt study drug discontinuation.

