4.6 Follow-Up

In Part 1A and Part 1B, after completion of study drug dosing, participants enter the follow-up period, i.e., visits 2 through 7, per the schedule in [Appendix 1](#).

In Part 2, after study drug discontinuation or completion of all 3 combination doses, participants enter the follow-up period, i.e., visits 7 through 9, per the schedule in [Appendix 1](#), if feasible. Visit 7 should be scheduled approximately 14 days after study drug discontinuation. Additional and/or more frequent safety laboratory tests may be performed as clinically indicated per the investigator's discretion.

In all study parts, if a participant is unable to complete the study but has not withdrawn consent, the EOSV (i.e., visit 8 in Part 1A and Part 1B, and visit 10 in Part 2) is conducted 30 days (+3 day window) after the last dose of study drug.

Participants may be classified as lost to follow-up after both of the following criteria are met:

- Failure of participant to respond or reply to 3 documented phone or electronic mail contact attempts.
- Failure of participant to respond to a certified letter.

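### Part 2: after dose 3 no laboratory panel for all participants falls inside the DLT window, so asymptomatic laboratory DLTs there are found mainly by discretionary testing

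*Protocol*

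**What the plan says.** Protocol Section 4.3: "The DLT period is defined as the period from initial infusion of study drug(s) through 2 weeks following the last study drug infusion". Laboratory findings count as DLTs. A related Grade 2 laboratory abnormality is exempt only if it lasts less than "72 hours and is not otherwise associated with clinical complications"; related Grade 3 or higher findings have no exemption.

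Section 4.1.3 gives Part 2 three combination doses two weeks apart and up to 6 participants. Two or more participants with a DLT suspend enrollment and dosing. SAP Section 3.4 repeats this rule.

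Appendix 1, Table 8 (Part 2) marks chemistry at Screening and Days 1, 15, 29 and 78. Hematology has the same marks plus Day 43, under footnote k: "Day 43 hematology is assessed only for participants undergoing leukapheresis". The footnote continues: "This hematology assessment is performed within the window for the scheduled leukapheresis". Footnote h says that, where a baseline procedure was done, "a second leukapheresis procedure is completed 2 weeks (+2 week window) following the final study drug infusion". Coagulation and urinalysis are marked at Screening and Day 78 only. For anything else, footnote i says "Additional and/or more frequent safety laboratory tests may be performed as clinically indicated", at the investigator's discretion.

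Section 4.6 places the visit concerned: "Visit 7 should be scheduled approximately 14 days after study drug discontinuation".

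**The concern.** The protocol counts laboratory abnormalities toward DLT over a window that closes two weeks after dose 3, yet it schedules no blood test for every participant between the day of dose 3 and the close of that window. For laboratory events after dose 3, a record of no DLT can therefore mean that nobody measured.

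Two uses of the data depend on this: the 2-of-6 suspension rule and the multi-dose tolerability conclusion. Part 2 is also the first repeat dosing of MGD020 in humans, since Section 2.3.1.1 reports no other clinical study. Adverse event review, vital signs and directed examination continue through follow-up, so symptomatic toxicity would be picked up. The gap concerns asymptomatic laboratory events.

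**Working it through.** Here a universal panel means chemistry and hematology scheduled for every participant.

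**The plan's own timeline.** Doses fall on Day 1, 1 + 14 = Day 15 and 15 + 14 = Day 29. The end-of-study visit is 7 weeks after the last dose: 29 + 49 = Day 78. The study period is (78 − 1)/7 = 11 weeks. Both agree with Section 4.1 and Table 8.

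**End of the DLT window.** 29 + 14 = Day 43.

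**Universal panels after the infusion day and within 14 days of it** (rows of Tables 7 and 8):

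| Dose | Panel days | Number |
|---|---|---|
| Part 1, single dose on Day 1 | 2 and 8 | 2 |
| Part 2, dose 1 on Day 1 | 15 | 1 |
| Part 2, dose 2 on Day 15 | 29 | 1 |
| Part 2, dose 3 on Day 29 | none | 0 |

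The documents do not say whether Day 29 blood is taken before or after the infusion. Either way it is a same-day sample and does not cover the two weeks after dose 3.

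**Length of the gap.** Chemistry: 78 − 29 = 49 days. With the visit windows (±1 day at Day 29, ±3 days at Day 78) the range is 75 − 30 = 45 to 81 − 28 = 53 days.

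**The leukapheresis blood count.** Its window is 29 + 14 = Day 43 to 29 + 28 = Day 57. It can fall on the last day of the DLT window or up to 14 days after it, and it includes no chemistry.

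**Later visits.** Day 78 is 78 − 43 = 35 days after the window closes. The early end-of-study visit, 30 to 33 days after the last dose, is 30 − 14 = 16 to 33 − 14 = 19 days after it. Either could show a persisting abnormality, but neither could place its onset inside the window.

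**What a Visit 7 panel would add.** An abnormality that starts *o* days after dose 3 is present at day 14 only if it lasts at least 14 − *o* days: 13 days for *o* = 1, 12 days for *o* = 2. To be present on Day 78, which is 49 days after dose 3, it must last at least 49 − *o* days: 48 or 47. The panel therefore adds detection of abnormalities lasting from about two weeks to about seven. It also dates the longer ones to the DLT period. It does not see those that resolve earlier. The documents give no rate for such events, so the gain cannot be expressed as a probability.

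**The case against.** **Other rules already act.** The suspension rule in Section 14.9 applies throughout the study: two participants with related Grade 3 or higher toxicity, or two with the same related toxicity at Grade 2 or higher. A persisting abnormality found on Day 78 can trigger it without any dating of onset, and it counts as a treatment-emergent event. This stands. A reader might infer that late laboratory findings are lost to the safety assessment, and the documents do not support that. What Section 14.9 does not replace is the 2-of-6 rule for combinations such as two different Grade 2 laboratory DLTs, or for events gone by Day 78.

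**The class of events is narrow.** The event must be asymptomatic, related and Grade 2 or higher. Under Section 12.2.1 it must also need intervention or suggest disease or organ toxicity, because the triggers tied to dosing no longer apply after dose 3. The related events listed for 21 single-dose MGD014 participants were all Grade 1, arose on the infusion day, and included no blood-test abnormality (Section 2.3.2.1). Monkeys given MGD020 weekly for 6 weeks had no hematology changes (Section 2.3.1.2.2). No later stage depends on Part 2. All of this stands and sets the size of the point.

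**No rule requires a panel at the end of the window.** Part 1, which does control escalation, has no scheduled panel on Days 9 to 15. That is correct, but Part 1 has two panels earlier in its window. Dose 3 in Part 2 has none after the infusion day.

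**A stronger reading about dose delays.** Section 4.4.1 says: "In Part 2, a dose delay of up to 7 days is allowed for drug-related or non-drug related AEs". A reader might infer that Visit 7 stays at Day 43 after a delayed dose 3 and so comes too early. Section 4.5 lists completion of planned dosing among the ways study drug ends, so Section 4.6 places Visit 7 about 14 days after the actual third dose for completers. The wording is loose mainly for someone who stops early for a reason other than an adverse event. Section 12.2.4.4 already follows adverse events that cause discontinuation.

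**Conclusion.** The point holds as a minor one, a cheap improvement. Dose 3 is the only dose in the study with no universal laboratory panel between the infusion day and the end of the DLT window. Apart from the optional-leukapheresis blood count, asymptomatic laboratory DLTs in those two weeks are found within the window only by discretionary testing.

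The impact is limited to up to 6 participants at one dose level, with no further drug due to them and no laboratory signal in the earlier data. This rests on nominal visit days and on the chemistry and hematology rows of Table 8 as they stand. Those rows agree with the footnotes and the dosing days.

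A reader might infer that the 2-of-6 rule is seriously weakened. The documents do not support this: they give no DLT rate and no indication of what share of DLTs would be asymptomatic laboratory events after dose 3.

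**What to change.** In Table 8:

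- Mark chemistry and hematology at Visit 7 (Day 43, existing ±2 day window) for all Part 2 participants, preferably drawn no later than 14 days after the last infusion.
- Delete the leukapheresis restriction in footnote k.
- Keep a separate blood count before the procedure when leukapheresis falls on a later date.

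As an optional clarification, tie Visit 7 in Section 4.6 to the last infusion rather than to study drug discontinuation. This matters mainly for participants who stop early for reasons other than an adverse event. The DLT definition in Section 4.3 needs no change.

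The cost is a schedule and footnote amendment for Part 2, plus one or two extra local-laboratory tubes per participant. Visit 7 already carries PK, IPDA/rca-RNA and SCA samples (Table 11) and possibly leukapheresis, and Section 10.3.4 notes that blood volume is a constraint. A day-14 panel will still miss abnormalities that resolve before it.
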